10.3.1 Ketorolac Concentration in Peritoneal Fluid - HPLC

Peritoneal concentrations of the R(-) and S(+) enantiomers of ketorolac will be determined by using published procedures for measuring plasma concentrations (44). High pressure liquid chromatography will be performed using UV detection at 313 nm. Standards will be prepared at 7 ketorolac plasma concentrations using 100 μ L steroid-free plasma to attain final concentrations of 0.025, 0.05, 0.10, 0.25, 0.5, 1.0, and 2.0 μ g/mL. Peritoneal samples (100 μ L) and standards will be added to silanized tubes containing the internal standard, loxapine HCL. Before extraction with 4 mL of methyl tert-butyl ether, proteins will be precipitated with 30 μ L of 10% weight to volume solution of trichloroacetic acid. Samples will be shaken for 10 min, centrifuged for 10 min, and the organic layer transferred to silanized culture tubes and evaporated under nitrogen. Mobile phase (50 μ L) will be added, the samples then will be transferred to autosampler vials, and 30 μ L will be injected onto the high pressure liquid chromatography column. Baseline separation of the isomers will be achieved using a chiral column (Astec Chirobiotic R (250 _ 4.6 mm²) obtained from Advanced Separation Technologies, Inc. Whippany, NJ) using a binary gradient mobile phase of 0.07 g ammonium formate and 24 μ L glacial acetic acid per liter methanol and increasing to 100% methanol for 17.5 min at a flow rate of 1.0 mL/min. Samples will be performed in duplicate.

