10.1 Pre-treatment Sample Collection

- Collection of ascites cells at the time of tumor debulking
- Collection of peritoneal fluid and cells by the PI ([name]) or the co-PI's ([name] and [name]) and blood prior to ketorolac administration.

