11.2 Endpoint Analyses

11.2.1 Primary Endpoint and Sample Size

Ketorolac availability, concentration and racemic mixture of Toradol® ([R,S]-ketorolac) in the peritoneal cavity. Intraperitoneal concentration and racemic mixture of ketorolac is currently unknown although serum pharmacokinetic data suggests a slower clearance of the R-racemate. The **primary objective** of this study is to determine the concentration of measurable levels of R and S- Ketorolac (and the percent racemic mixture) in the peritoneal cavity after IV administration in the post-operative patient after cytoreductive surgery. Since this is a pilot trial for feasibility of obtaining the desired measures, a true sample size calculation is difficult to assess. We anticipate that we will need to recruit 60 patients pre-operatively who meet the first phase of eligibility. We anticipate that 60% will have a diagnosis other than advanced stage invasive epithelial ovarian cancer, fail optimal debulking, have a clinical decision to not proceed with a port placement or not enough ascites or negative cytology of the ascites that will warrant no further participation in the study. This data is based on our initial experience with the first 12 patients enrolled on the trial. We then anticipate that 25 patients will have intraoperative port placement and be eligible for secondary eligibility. We anticipate that an additional 15-18 patients will either fail secondary eligibility, decline sample collection, decline ketorolac or have indications to withhold ketorolac, decline blood sampling, have inadequate re-accumulated fluid for sampling, or failed extraction of ascites samples from the port. The sample target remains 7-10 complete sets of blood and ascites samples for primary and secondary endpoint analyses.

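### Peritoneal ketorolac, the primary endpoint, is read off plasma-only standards, and no check is stated that recovery in post-operative peritoneal fluid is the same

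*Combined protocol and SAP*

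**What the plan says.** Section 11.2.1 gives the primary objective: to "determine the concentration of measurable levels of R and S- Ketorolac (and the percent racemic mixture) in the peritoneal cavity".

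Section 10.3.1 measures this "using published procedures for measuring plasma concentrations". The calibration set is described as "Standards will be prepared at 7 ketorolac plasma concentrations", made up in 100 µL of "steroid-free plasma to attain final concentrations of 0.025, 0.05, 0.10, 0.25, 0.5, 1.0, and 2.0" µg/mL. Peritoneal samples of 100 µL go through the same steps.

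The section has three safeguards:
- An internal standard goes in with samples and standards alike: "standards will be added to silanized tubes containing the internal standard, loxapine HCL".
- Protein is precipitated with trichloroacetic acid before solvent extraction.
- Samples are run in duplicate.

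It names no standards or quality controls in peritoneal fluid, no spike-recovery check and no validation in that fluid.

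Drug-free peritoneal fluid is already part of the plan. Section 10.1 lists "Collection of peritoneal fluid and cells by the PI" before dosing, and section 10.3 sets 10-20 cc per time-point, predose included. Section 4.2 excludes off-study ketorolac or other NSAIDs before the study dose. Sections 10.3.2 and 10.3.3 use predose fluid as a control in the GLISA and CYTOO assays; section 10.3.1 does not use it for HPLC.

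**The concern.** A method set up for plasma is applied to a different fluid. Section 1.5.2 says the racemate is 99% protein bound and expects serum albumin to fall after surgery. The assay removes protein before extracting the drug. If post-operative peritoneal fluid differs from plasma in protein content (plausible, but the documents give no figure), the fraction of drug recovered could differ too, and a plasma curve would then misstate the peritoneal concentration.

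The result at stake is the absolute concentration. Section 1.5.2 calls the intraperitoneal distribution unknown, so no earlier value exists against which a biased result would stand out. Readers will naturally set the peritoneal level beside the paired blood level, or beside the estimated migration IC50 of 7 µM for R-ketorolac in Table 1. Duplicates share the same curve and cannot expose the error. If recovery also varied between patients, it would add noise to the peritoneal R-ketorolac values used in the trend analyses of section 11.2.2.

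**Working it through.** **1. The plan's own figure.** The documents give no recovery or assay-bias figure to reproduce. The relevant sample size is the 7-10 complete sets in section 11.2.1. Of 60 recruited with 60% lost, 60 × 0.40 = 24 remain, against the stated 25. Then 25 - 18 = 7 and 25 - 15 = 10. The target reproduces, and the steps below use n = 7 and n = 10.

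**2. What passes through the internal standard.** Let the signal be the ratio of ketorolac to loxapine. With recovery ρ in each fluid, measured = k × true, where

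k = (ρ_ket / ρ_lox in peritoneal fluid) ÷ (ρ_ket / ρ_lox in plasma).

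If loxapine tracks ketorolac in both fluids, k = 1 and there is no bias. Only the part of a difference that loxapine does not share remains. The documents do not give k.

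**3. Which results k touches, if it is common to all peritoneal samples.**
- Absolute concentration: multiplied by k. For an assumed k of 0.8 to 1.2, the shift is -20% to +20%.
- Repeated-measures ANOVA and Tukey comparisons of concentration: numerator and denominator scale together, so F and the p-values are unchanged.
- Ordering of R-ketorolac values for the trend analyses: unchanged.
- R percentage: with equal recovery, 0.6k / (0.6k + 0.4k) = 0.60 for any k. With unequal recovery (assumed 0.8 for R, 0.9 for S), a true 50% becomes 0.40 / (0.40 + 0.45) = 47%; with the values reversed, 53%.

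**4. Bias against sampling error.** No peritoneal variability is given. As a stand-in, take the 30 mg row of Table 2 (plasma), reading ± as a standard deviation: 0.7/4.65 = 15%, 0.7/2.17 = 32%, 0.7/1.04 = 67%. The 95% half-width relative to the mean is t(0.975, n-1) × CV / √n. At n = 7 and CV 15% this is 2.447 × 0.15 / 2.646 = 0.139. Coverage of the true mean by the usual 95% t-interval was simulated with 200,000 normal samples per row:

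| CV | n | Half-width | Coverage, no bias | Coverage, -10% | Coverage, -20% |
|---|---|---|---|---|---|
| 15% | 7 | 14% | 95% | 62% | 5% |
| 15% | 10 | 11% | 95% | 45% | 0.4% |
| 32% | 7 | 30% | 95% | 88% | 59% |
| 32% | 10 | 23% | 95% | 83% | 40% |
| 67% | 7 | 62% | 95% | 93% | 87% |
| 67% | 10 | 48% | 95% | 93% | 82% |

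Going from 7 to 10 patients narrows the interval around the wrong value. The biases in this table are assumed; it shows what a bias would do, not that one exists.

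**5. Is there enough predose fluid?** Per patient or pool:
- duplicate seven-point curve: 7 × 0.1 mL × 2 = 1.4 mL
- blank: 0.2 mL
- predose HPLC sample: 0.1 mL × 2 = 0.2 mL
- GLISA control: 0.5 mL × 2 = 1.0 mL
- CYTOO control on up to four cell lines, taking 0.5 mL each: 2.0 mL

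The total is 4.8 mL, against 10-20 mL where the full draw is obtained.

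**The case against.** The internal standard is the strongest reply. It enters samples and standards before precipitation and extraction, and its purpose is to offset differences in loss. Acid precipitation should also reduce dependence on protein binding. A reader might infer from the plasma curve that any recovery difference passes in full into every peritoneal value; the documents do not support that, because only the part loxapine does not share would pass. What stands is that nothing shows how well loxapine follows ketorolac in this fluid.

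Second, the mechanism is unproven. The 99% binding figure comes from the general pharmacology section and is not a peritoneal measurement. The source method is a cited publication, and recovery data could also sit in a laboratory procedure outside the protocol. This is why the point is limited to an unstated check.

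Third, the damage is narrow. This is a feasibility pilot; section 11.2 sets no decision threshold and no peritoneal-to-serum ratio, and GLISA and CYTOO test the fluid's bioactivity separately. That is correct, and it confines the exposure mainly to the absolute concentration and how readers interpret it. That concentration is nonetheless the stated primary objective.

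Fourth, calibration in predose fluid might be taken to eliminate the error. It would not: fluid composition may vary between patients and may change by 24 or 48 hours, so a pooled predose blank need not match a later individual sample.

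**Conclusion.** The point holds as an optional improvement to the assay of the primary endpoint, not as a demonstrated flaw. The plan calibrates peritoneal samples in plasma only and states no check that recovery is the same. Any uncorrected difference would bias the absolute peritoneal concentrations by an unknown amount. The ±20% range and the coverage figures rest on assumed biases and on variability borrowed from plasma.

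It would be wrong to conclude that the pre/post tests or the racemic percentage are invalid. The tests are unaffected by a proportional bias common to the samples, and the percentage moves only if the two enantiomers recover unequally. The sample size does not change.

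**What to change.** In section 10.3.1, keep the plasma curve for serum. For peritoneal samples, prepare the seven standards in pooled predose peritoneal fluid, with a blank to confirm that it is drug-free. At minimum, include low, mid and high spiked controls in that fluid in each run. Report recovery relative to plasma for each enantiomer, and correct the peritoneal concentrations if recovery falls outside a limit set in advance. Where volume allows, spike a subset of later samples too, because predose fluid may not represent fluid at 24-48 hours.

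The cost is laboratory work. A duplicate seven-point curve adds 7 × 2 = 14 preparations and about 1.4 mL of pooled fluid per run; three control levels in duplicate add 3 × 2 = 6 preparations and 0.6 mL. No extra patient sampling is needed, but enough fluid must be pooled first. Section 11.2.1 expects some patients to have too little re-accumulated fluid or failed extraction, so predose fluid may be limited. Where it is, the spiked controls are the practical form.

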10.3.2 GTPase Inhibitory Activity of Peritoneal Fluid

Rac1 activity will be measured in cells using effector binding assays (GLISA) that are commercially available (Cytoskeleton, Inc) as an independent measure that there is sufficient bioactive R-ketorolac in the peritoneal fluid to inhibit GTPase activity in cultured cells (as illustrated in Fig 3A, ketorolac panel). Because Rac1 inhibition is most robust we will focus on this GTPase. 3T3 cells will be cultured without serum in 6-well dishes in duplicate and subsequently incubated with 500 μ L/well peritoneal fluid from each time-point for 1 hour prior to stimulation with 10 ng/ml EGF for 2 minutes 3T3 cells will be harvested, lysed and assayed for activated Rac1 GTPase per manufacturer's instructions. Results will be reported as ng Rac1-GTP normalized to +EGF drug samples. Controls will be included to monitor EGF responsiveness of Rac1 activation and ketorolac inhibition of Rac1 activation. Negative controls: peritoneal fluid prior to ketorolac treatment and cells without EGF stimulation. Positive controls: 1 ng purified Rac1-GTP; +EGF treated cells with serum in lieu of peritoneal fluid; cells treated with 100 μ M R-ketorolac or S-ketorolac for one hour as shown in Fig. 3A.

10.3.3 Efficacy of Peritoneal Fluid containing Ketorolac in Inhibiting Cell Adhesion and Spreading in Vitro.

The peritoneal fluid will be tested on immortalized cells in vitro as an alternate measure that there is sufficient bioactive R-ketorolac in the fluid to inhibit the adhesion/migration of immortalized mouse Swiss 3T3 or human ovarian cancer cells (OvCa429, SKOV or OvCa433) in culture. The assay will utilize CYTOO micropatterned chips that are coated with fibronectin in defined patterns (144 micropatterns/sector with 12 sectors/chip) (Fig. 7). Immortalized cells will be mixed with 500 μ L/5 \times 10³ immortalized cells that have been

Fig. 7. Cytoo micropatterned chips for analysis of cell adhesion and spreading. Chips have arrays of adhesive patterns as illustrated in red that enable cells to adhere and spread into characteristic shapes. The chips have 144 micropatterns/sector, there are four different shapes arrayed in three sizes (small, medium and large). Thus, a single chip allows the analysis of >1700 cells. We have tested cell shape changes in response to EGF stimulation +/- a Cdc42 inhibitor. Inhibition of Cdc42 caused cells to look like unstimulated control cells, and fail to adopt a migratory phenotype + EGF that was readily quantified using the chips (not shown).

trypsinized and washed with PBS⁺. The mixture will be allowed to adhere to a CYTOO chip for 15-60 min. Cells will be fixed directly, imaged and evaluated for cell number and cell shape on each of four micropatterns. It is expected that the presence of R-ketorolac will reduce speed of cell adhesion and or cell spreading on the substrate. Positive controls: peritoneal fluid prior to ketorolac treatment; cells in serum in lieu of peritoneal fluid; Negative controls: cells plated in the presence of 100 μ M R-ketorolac or S-ketorolac for one hour prior.

10.3.4. Spreading, Adhesion, and Migration Assays of Patient Derived Peritoneal Cells

The impact of ketorolac treatment on residual ovarian tumor cell behavior will be assessed by measuring time for cell adhesion and spreading, as well as migration distance as follows. All of the assays require only small numbers of cells. CYTOO chips (see 5.6.5 and Fig. 7) will serve as an alternate measure for assessing cell adhesion and spreading. Controls: patient cell adhesion prior to treatment; cell adhesion when incubated with 100 μ M R-ketorolac.

10.3.4.1. Spreading: Cells (100-5,000/sample) will be rinsed in Dulbecco's PBS (DPBS) and plated on coverslips without or with extracellular matrix coating and images will be obtained at regular intervals. Spreading is defined as flattened cells without the refractile, fibroblastic morphology determined and expressed as a percentage of the total cells \pm SD.

10.3.4.2. Adhesion: Cells (100-5,000/well) will be plated onto 96 well plates without or with extracellular matrix coating and incubated for 30 min. Cells will be fixed and non-adherent cells will be removed by gentle washing. Colorimetric quantification of adherent cells will be performed using standard protocols.

10.3.4.3 Migration: Cells (100-5,000/sample) will be placed on collagen-coated coverslips in culture medium and migration will be measured by time lapse photography on a heated microscope stage (UNM Microscopy Facility). Distance traversed for individual cells will be quantified by image analysis software.

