2.2 Secondary Objectives

The secondary endpoint of this study is to determine the effect of IV ketorolac on cell adhesion and migration of ovarian cancer cells retrieved from the peritoneal cavity after cytoreductive surgery

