10.2 Post-treatment Sample Collection

- Collection of peritoneal fluid after ketorolac administration will be done at select time-points after ketorolac administration (1 hour, 6 hours, and 24 hours) an additional 48 hour sample (after the initial dose) will be done in patients having elective multiple ketorolac dosing.
- Cells and effluent will be separated from fluid at the above select time-points (1 hour, 6 hours, 24 hours) and at 48 hours after the initial ketorolac dose in patients who receive elective multiple ketorolac dosing.

10.3 Pharmacokinetic Evaluation:

Blood and 10-20 ccs of peritoneal fluid will be retrieved at the following time-points. Serum will be isolated and peritoneal fluid will be isolated from cellular material via centrifugation.

Timepoint	Time after ketorolac
1	Predose
2	1 hour
3	6 hours
4	24 hours
5	48 hours*

* elective time-point for patients receiving clinically indicated multiple dosing of ketorolac

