10.3.5. PCR analysis of Patient Derived Peritoneal Cells

Genes downstream of Rac1 and Cdc42 activation, which have been validated in cell culture and through in vivo studies (e.g. PAK, IQGAP, DOCK-180, CRK, WAVE3) will be tested by quantitative real time PCR using human genome predesigned and validated primer sets and assay kits from Origene (Rockville, MD). Each assay will be performed in duplicate and ketorolac response will be established by comparison of pretreatment versus treatment samples. A >2-fold change between 0 treatment and subsequent treatment time-points

would be considered significant. This assay will be performed only when sufficient cell numbers are present in the peritoneal fluid (>10,000 cells) to allow purification of RNA.

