11.2.2 Secondary Endpoints

We will determine the effect of IV ketorolac on cell adhesion and migration on ovarian cancer cells retrieved from the peritoneal cavity after cytoreductive surgery using several different biologic assays. Isolated cells will be tested for evidence of target inhibition and functional changes in adhesion and migration. Target activity assays: Rac1 and Cdc42 activity will be measured in cells using effector binding assays (GLISA) that are

commercially available (Cytoskeleton, Inc) and are used to determine activity of primary cells ex vivo as we have demonstrated in (Fig. 1C). In addition, we will conduct qRT-PCR analysis of cells isolated pre and post ketorolac administration to test for expression of genes downstream of Rac1 and Cdc42 activation that were validated in cell culture and in vivo studies. Adhesive properties of cells will be measured by assays for spreading and adhesion. For spreading analysis, cells will be rinsed in Dulbecco's PBS (DPBS) and plated on coverslips without or with extracellular matrix coating and images will be obtained at regular intervals. Spreading is defined as flattened cells without the refractile, fibroblastic morphology determined and expressed as a percentage of the total cells \pm SD as we've described previously (46). For adhesion, cells will be plated onto 96 well plates without or with extracellular matrix coating and incubated for 30 min. Cells will be fixed and non-adherent cells will be removed by gentle washing. Colorimetric quantification of adherent cells will be performed using standard protocols. Migration will be measured after plating cells on collagen-coated coverslips in assessing migration by time lapse photography on a heated microscope stage (UNM Microscopy Facility). Distance traversed for individual cells will be quantified by image analysis software. Data will be analyzed as a repeated measure ANOVA followed by Tukey's post hoc analysis in order to evaluate whether there are significant differences between groups (pre-and post-ketorolac treatment). Trend analyses of response will also be performed based on peritoneal R-ketorolac concentrations.

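### The secondary endpoint is stated for ovarian cancer cells, but the assays on patient-derived cells are read on all cells recovered from peritoneal fluid, with no record of how many are tumour cells

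*Combined protocol and SAP*

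**What the plan says.** **Target.** Section 2.2 sets the secondary objective as the "effect of IV ketorolac on cell adhesion and migration of ovarian cancer cells retrieved from the peritoneal cavity after cytoreductive surgery". Section 10.3.4 opens: "The impact of ketorolac treatment on residual ovarian tumor cell behavior will be assessed by measuring time for cell adhesion and spreading". Section 11.2.2 repeats the ovarian cancer target and then states: "Isolated cells will be tested for evidence of target inhibition and functional changes in adhesion and migration".

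**How cells are obtained.** Section 10.2: "Cells and effluent will be separated from fluid at the above select time-points (1 hour, 6 hours, 24 hours"), with a 48-hour sample added for patients on multiple dosing. Section 10.3: "Serum will be isolated and peritoneal fluid will be isolated from cellular material via centrifugation".

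**What is read.**
- Spreading (10.3.4.1): "morphology determined and expressed as a percentage of the total cells".
- Adhesion (10.3.4.2): a colorimetric measure of whatever adheres in the well.
- Migration (10.3.4.3): distance travelled by single cells, with no rule for which cells are tracked.
- qPCR (10.3.5): a change above 2-fold counts as a response. The gate is a cell count: "This assay will be performed only when sufficient cell numbers are present in the peritoneal fluid (>10,000 cells").
- GLISA on patient cells (11.2.2): Rac1 and Cdc42 activity in the isolated cells.

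**Nearest safeguard.** Section 11.2.1 lists negative ascites cytology among several reasons why recruited patients will go no further.

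**Analysis.** Section 11.2.2 plans repeated-measures ANOVA with Tukey comparisons of pre- and post-dose values, plus a trend analysis on peritoneal R-ketorolac concentration. Neither has a term for cell composition.

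**The concern.** Spinning separates cells from fluid. It does not separate tumour cells from the other cells in the fluid. If the read-outs are followed as written, the trial measures a mixture of unknown composition and reports it as the behaviour of cancer cells.

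Two errors can follow. If other cells respond less than tumour cells, a real effect is diluted and may be missed. If the mix changes between the pre-dose and post-dose samples, the average changes without any drug effect, and there is no untreated group to show it. Section 10.1 lists two pre-treatment cell collections, one at debulking and one just before ketorolac. Sections 10.3.4 and 10.3.5 do not say which is the baseline, although the pre-dose row in the 10.3 schedule points to the second.

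At stake is whether the secondary result can be stated for ovarian cancer cells at all.

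**Working it through.** **1. The plan's own figures.** No tumour fraction, effect size, SD, alpha or power is stated for this endpoint, so there is no such figure to reproduce. The number of sample sets can be checked from Section 11.2.1: 60 × (1 − 0.60) = 24, against the stated 25; then 25 − 18 = 7 and 25 − 15 = 10, which gives the 7–10 complete sets.

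**2. Search for tumour-cell identification.**
- Sections 4.1 and 4.2 require an epithelial diagnosis on frozen section. That describes the patient.
- The cytology remark in 11.2.1 also describes the patient, and it is not an eligibility criterion. It says nothing about the pre-dose, 1, 6, 24 or 48 h samples.
- The 100 µM R-ketorolac control in 10.3.4 shows whether the mixture can respond. It does not correct for a change in the mixture.
- No marker, sorting, depletion, post-operative cytology or minimum tumour fraction is given in 10.3.4, 10.3.5 or 11.2.2.

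All inputs in steps 3 to 5 are assumptions, because the documents supply none. Let f be the tumour-cell fraction.

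**3. Dilution.** With equal baseline values in both cell types, observed change = f × (tumour change) + (1 − f) × (other-cell change). Take f = 0.2 and a 50% fall in tumour cells:
- other cells do not respond: 0.2 × 50% = 10%
- other cells fall by 25%: 0.2 × 50% + 0.8 × 25% = 30%
- other cells fall by 50%: 50%, so no dilution.

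For qPCR, take a true 4-fold fall in tumour cells, with equal baseline expression and no response elsewhere. The observed level is 0.25f + (1 − f):
- f = 0.8: 0.40, a 2.5-fold fall
- f = 2/3: 0.50, a 2.0-fold fall
- f = 0.5: 0.625, a 1.6-fold fall.

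The >2-fold rule is therefore missed at a fraction of about two thirds or below.

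For power, use a paired t test at two-sided 5% as a simple stand-in for the planned ANOVA, with noncentrality (effect/SD) × √n. An effect with 80% power in pure tumour cells (standardised effect 1.27 at n = 7, 1.00 at n = 10) has about 30% power at f = 0.5 and 9% at f = 0.2, if the SD is unchanged and other cells do not respond.

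**4. Shift in mix, no drug effect: spreading.** Percent spread = f × (tumour rate) + (1 − f) × (other rate).
- Rates 60% and 10%, f from 0.7 to 0.3: 0.7 × 60 + 0.3 × 10 = 45%; 0.3 × 60 + 0.7 × 10 = 25%; change −20 points.
- Rates 70% and 30%, f from 0.6 to 0.4: 54% to 46%; change −8 points.
- Rates 60% and 40%, f from 0.6 to 0.4: 52% to 48%; change −4 points.

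With the same paired t test and an assumed SD of change of 15 points, a 20-point artefact is declared significant in 83% (n = 7) to 96% (n = 10) of trials. An 8-point artefact is declared significant in 22% to 33%.

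**5. Shift in mix, no drug effect: qPCR.** For a gene expressed k times higher in tumour cells, apparent fall = [k·f₀ + (1 − f₀)] / [k·f₁ + (1 − f₁)].
- k = 5, 0.7 to 0.3: 3.8 / 2.2 = 1.73-fold; does not pass.
- k = 5, 0.8 to 0.2: 4.2 / 1.8 = 2.33-fold; passes.
- k = 5, 0.6 to 0.2: 3.4 / 1.8 = 1.89-fold; does not pass.
- k = 10, 0.6 to 0.2: 6.4 / 2.8 = 2.29-fold; passes.

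The artefact crosses the >2-fold rule only with a large shift or a strong expression difference.

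**The case against.** The best case for the plan has five parts.

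- **Other assays support the biology.** Sections 10.3.2 and 10.3.3 apply patient fluid to cultured 3T3 or ovarian cancer lines, where patient cell mix does not arise. This stands, and the point excludes them. They test the fluid, however, not the patients' own cancer cells.
- **The shift examples are really about the missing control.** A time-matched untreated group would largely cancel a shift unrelated to drug. This stands. The shift matters here because there is no such group. Dilution would remain even with one.
- **Other cells may respond too.** The protocol itself uses 3T3 cells to detect Rac1 inhibition. If other peritoneal cells respond as strongly as tumour cells, dilution disappears, as step 3 shows. This limits the size. It does not establish what the mixture contains.
- **An isolation step may exist but not be written down.** The centrifugation sentence sits in the pharmacokinetic section, and the spreading method rests partly on a cited paper. The supportable statement is therefore that tumour-cell content is unspecified. If a step exists, writing it into the protocol would go far to answer the point. Even so, the written denominator for spreading is all cells.
- **This is a pilot, the endpoint is secondary and cells are scarce.** All true, and the fix is limited accordingly. The plan still tests for significance and applies a response threshold to these data.

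**Conclusion.** The point holds for the assays on patient-derived cells in 10.3.4, 10.3.5 and 11.2.2: the endpoint names ovarian cancer cells, and the read-outs as written cover all recovered cells. The mismatch comes from the text alone. Its numerical effect does not: it rests on assumed tumour fractions, rates and expression ratios, and ranges from no dilution to a 50% fall showing as 10%, and from a 4-point to a 20-point spurious change in spreading.

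A reader might infer more than the documents support:
- **That every laboratory assay is compromised.** The cultured-line assays are not.
- **That the wrong cells are measured.** The cells are mixed in unknown proportion, and tumour cells may predominate.
- **That the patients sampled have the least residual tumour.** Failed optimal debulking is only one of several pooled attrition reasons in 11.2.1 and is not an eligibility criterion. Section 1.1 describes optimal debulking as residual tumour up to 1 cm, not none. The cytology remark points the other way.
- **That a change in mix will readily trip the >2-fold rule.** At 70% to 30% with a 5-fold ratio it does not.
- **That the false-effect risk is independent of the missing control group.** It is not.

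**What to change.** In 10.3.4, 10.3.5 and 11.2.2, where cell numbers allow, record the tumour-cell fraction of each pre- and post-dose sample:
- for imaged assays, apply an epithelial tumour marker to the coverslips or chips already made, once fixed after the last image;
- for bulk assays (plate adhesion, qPCR, GLISA), take a small aliquot of the same sample.

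Report the fraction beside each result. Base any cancer-cell conclusion on marker-positive cells, or on pre/post pairs with both fractions documented. State which pre-dose collection is the baseline.

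Where this is not done, word the endpoint and conclusion in 2.2 and 11.2.2 as concerning peritoneal cells, and draw no conclusion about ovarian cancer cells. The headings of 10.3.4 and 10.3.5 already use that term.

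**Cost.** An extra laboratory stain and no new patient procedure. The assays in 10.3.4 use 100–5,000 cells and qPCR needs more than 10,000, so an aliquot competes for scarce material. For migration, stained cells must be matched to their recorded tracks. Some of the 7–10 sets will lose evaluable pairs. The wording change costs nothing.
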